### **Post study Follow-up Period**

All patients will be followed every 12 months by study personnel after the EoT. Any treatment beyond the EoT is at the discretion of the treating physicians. The primary or secondary endpoints will be collected every 12 months since the EoT by telephone interview.

## 17. Management of Ischemic Events with Temporary Signs during Follow-up

If a patient in either treatment arm develops a potential clinical neurological event (TIA, ischemic stroke), an adjudication packet will be produced by the site within 72 hours. Vascular imaging including angiography will be at the discretion of study neurosurgeon. If primary endpoint occurs, MRI will be performed. Since the most effective therapy is unknown for MMD patients with frequently TIA or recently ischemic stroke, it will be not recommended for patients to receive multimodal neuronavigation bypass or empirical bypass. However, the patient's risk factors should be in target goals.

If patients in the both arms experience TIA or ischemic stroke postoperatively associated with MRI proven infarctions, continued medical therapy alone for them will be recommended by study investigators consisting of neurosurgeons. Decompressive craniectomy will be not recommended to patients without risk of cerebral hernia who have an ischemic stroke.

Additionally, if patients have reached a primary endpoint, that is, stroke in the territory of surgery side, any treatment after occurrence of stroke will be not monitored by investigators and at the discretion of treating physicians.

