## **6. Study Endpoints**

### **6.1. Primary Endpoint**

All strokes & death within 30 days post-surgery and ipsilateral hemorrhage afterwards

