## **16. Schedule of Follow-up and Post-study Follow-up Period**

All patients will be followed up until the primary endpoint or the end of the trial. Complete endpoint information will be obtained with the best effort irrespective of

patient study status, unless patients withdraw consent to participate the trial. Patients will continue to be followed up beyond date of consent withdrawal if they stop the trial and receive other treatment such as medical therapy but agree to provide the prognostic information. The face-to-face interview will be performed by study neurologists at discharge, at 3 months, at 6 months and at 12 months (or by telephone) after the recruitment of patients. If they are more convenient to have access to the study site near to their living areas, patients will be allowed to go to the site for their follow-up.

Visits	Windows	Definition
Randomization	0 day	Study Day 0 day
At discharge	0 day	Based on the number of hospitalization days
At 3 month	7 days	Day 83-97
At 6 months	14 days	Day 166-194
At 12 months	30 days	Day 330-390

Note: 1 month= 30 days

The following procedures will be done at 3 months, at 6 months after enrollment:

- ✧ A neurological evaluation will be performed (Modified Rankin Scale, National Institute of Health Stroke Scale, modified Barthel Scale);
- ✧ A physical examination will be performed, including vital signs (blood pressure, heart rate);
- ✧ Information will be collected on medications, risk factors, and events of interest since the last visit;
- ✧ Computed Tomography Perfusion (CTP), Magnetic Resonance (MR) and Digital subtraction angiography (DSA) will be performed;

The following evaluations will be done at the end of trial:

- ✧ Lab tests for diabetic control and hyperlipidemia management will be performed;
- ✧ A neurological evaluation will be performed (Modified Rankin Scale, National Institute of Health Stroke Scale, modified Barthel Scale);
- ✧ A cognitive function evaluation will be performed (MoCA);
- ✧ Computed Tomography Perfusion (CTP) and Magnetic Resonance (MR) will be done if a patient does not experience a primary endpoint before the end of trial. Images will be transferred to the core imaging evaluation lab.
- ✧ Information will be collected on medications, risk factors, and events of interest since the last visit;

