## APPENDIXS

### Study Design Chart

**Study Flow Chart**

**Schedule of Visits and Tests**

	Visit 1	Visit 2	Visit 3	Visit 4	Visit 5	Visits after 1 year	Event visit
Assessments	Screening/Randomize	At discharge	At Day 90 ±7d	At Day 6 months ±14	At 1 year ± 1 month	Every 12 months ±1 month	
Informed Consent	X						
Eligibility criteria	X						
Patient Randomization	X						
Relevant medical history	X						
Demographics	X						
MRI	X						
CTP	X						
DSA before Surgery							
Vital signs	X						X
Modified Rankin Score	X	X	X	X	X	X	X
NIHSS	X	X	X	X	X		X
Modified Barthel Score	X	X	X	X	X		X
Process Core Labs	X						
MRI after surgery		X	X	X	X		
CTP after surgery		X	X	X	X		X
DSA after surgery		X	X	X			X
Compliance reminder			X	X	X	X	X
Current Medications	X	X	X	X	X	X	X
Risk factor Management	X		X	X	X	X	X
AEs, SAEs and Endpoints		X	X	X	X	X	X

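### Section 17 describes the primary endpoint differently from Section 6.1, although treatment monitoring, end-of-trial imaging and length of follow-up all depend on that term

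*Protocol*

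**What the plan says.** Section 6.1 defines the primary endpoint as "All strokes & death within 30 days post-surgery and ipsilateral hemorrhage afterwards". The synopsis and the primary aim in Section 4 repeat that definition.

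Section 17, which covers ischemic events during follow-up, reads differently. Its last paragraph begins "if patients have reached a primary endpoint, that is, stroke in the territory of surgery side" and continues that "any treatment after occurrence of stroke will be not monitored by investigators and at the discretion of treating physicians". The paragraph before it deals with TIA or ischemic stroke after surgery with infarction proven on MRI, and says that "continued medical therapy alone for them will be recommended by study investigators".

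Section 21.7 states the efficacy boundary for a primary endpoint described as stroke or death over one year.

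Section 16 makes the term operational. "All patients will be followed up until the primary endpoint or the end of the trial", and end-of-trial CTP and MR "will be done if a patient does not experience a primary endpoint before the end of trial". The next sentence on follow-up points the other way: "Complete endpoint information will be obtained with the best effort irrespective of" the patient's study status, unless consent is withdrawn. The Schedule of Visits and Tests marks "Current Medications", adverse events and endpoints at the later visits and at the event visit.

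**The concern.** A primary endpoint needs one definition, above all where conduct rules depend on it. Section 17 is where a site will look after an ischemic event, and its description is not that of Section 6.1.

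The patient who matters is one with an ischemic stroke on the operated side after day 30. Section 17 says that this patient has reached the primary endpoint; Section 6.1 says not. The event is also absent from the clinical events named in Section 6.2, which are contralateral infarction and operated-side TIA. The patient is still at risk of hemorrhage on the operated side, the only primary component after day 30, and still contributes to the mRS, NIHSS, Barthel and CBF comparisons at month 12.

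If the site follows Section 17, treatment monitoring stops. If it also carries that wording into Section 16, the month-12 CTP and MR are not done and follow-up may end early. Under Section 21.8 the patient would then be censored at the last contact at which all components were assessed, and the cause of the censoring would be a disease event.

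**Working it through.** The protocol states no figure on this point, so the check is a comparison of text, followed by a projection for scale.

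**Which events count under each description**

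| Event | Section 6.1 | Section 17 | Section 21.7 |
|---|---|---|---|
| Operated-side stroke, day 10 | yes | yes | yes |
| Stroke elsewhere, day 10 | yes | no | yes |
| Death without operated-side stroke, day 10 | yes | no | yes |
| Operated-side ischemic stroke, day 100 | no | yes | yes |
| Operated-side symptomatic hemorrhage, day 100 | yes | yes | yes |
| Stroke elsewhere, day 100 | no | no | yes |
| Death without operated-side hemorrhage, day 100 | no | no | yes |

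Section 17 is narrower than Section 6.1 up to day 30 and wider afterwards. Section 21.7 is wider after day 30. The appendix defines ischemic and hemorrhagic stroke separately, so the fourth row is a true conflict and not a matter of terminology.

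**What depends on the term**

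1. Treatment monitoring stops (Section 17).
2. Follow-up runs to this event or the end of the trial (Section 16).
3. End-of-trial CTP and MR are conditional on its absence (Section 16).

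Item 1 follows from Section 17 alone. Items 2 and 3 affect the day-100 patient only if the Section 17 wording is read into Section 16.

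**Scale**

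Inputs, all from Section 3: about 4% stroke risk per hemisphere in the first 30 days; 96% stroke-free over the following 5 years; and, in another series, 10.1% stroke risk at 2 years after surgery. I assume 100 patients, one operated hemisphere each, and a constant hazard from day 30 to day 365 (335 days).

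- Early strokes: 0.04 × 100 = 4.
- Late strokes, low: yearly hazard = −ln(0.96)/5 = 0.00816; risk = 0.96 × (1 − exp(−0.00816 × 335/365)) = 0.0072, or 0.7 per 100.
- Late strokes, high: yearly hazard = −ln(0.899/0.96)/(700/365) = 0.0342; risk = 0.96 × (1 − exp(−0.0342 × 335/365)) = 0.0297, or 3.0 per 100.
- Chance of at least one late stroke among 100: 1 − (1 − 0.0072)^100 = 0.51 and 1 − (1 − 0.0297)^100 = 0.95.

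If the constant hazard is dropped and the whole excess over the early risk falls in year 1, the figure is 10.1 − 4 = 6.1 per 100.

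These are late strokes of any type and side. At any given rate they are an upper bound for operated-side ischemic strokes.

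**The case against.** A reader might infer that the protocol releases these patients, so that their later hemorrhages go uncaptured, their rescue treatment goes unrecorded and informative censoring is built in. The documents do not support that.

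- Section 17 ends the monitoring of treatment. It does not end visits, endpoint collection or adjudication.
- Section 16 asks for endpoint information whatever the patient's study status, and all patients are to be contacted yearly after the end of the trial.
- Section 16 and the visit schedule still collect medications and events at the later visits.
- Section 21.8 has no rule that censors at an ischemic stroke.
- Section 21.3 counts only events adjudicated by the events committee, so a site's reading of Section 17 does not decide what is analyzed as a primary event.
- Under the Section 6.1 definition, Section 16 itself keeps the day-100 patient in follow-up.

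All of this stands. The losses are risks from conflicting text, not stated rules.

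The mismatch before day 30 also does little practical harm. After a contralateral stroke on day 10, Section 17 simply leaves treatment monitoring in place, and a section on ischemic events has some reason not to mention death. The two treatment paragraphs can be read together, one as a recommendation and the other as discretion, though the text does not say how they fit.

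The projection has limits too. It mixes series, and one of the two sources for the low figure is, by its title, a study of children, whereas this trial enrolls adults. A missed primary event would need a later operated-side hemorrhage in the same patient, for which the protocol gives no rate.

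What the objection does not remove is the contradiction itself, the halt to treatment monitoring on a definition that Section 6.1 does not share, and the conditional imaging. The best-effort sentence covers endpoint information; it does not restore month-12 CTP and MR or say which definition governs.

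**Conclusion.** The point holds as a contradiction with operational effect. Section 17 departs from Section 6.1 in both directions, and Section 21.7 adds a third version. The direction that matters is the late operated-side ischemic stroke: a site following Section 17 may stop monitoring treatment, omit month-12 imaging and possibly shorten follow-up in a patient with no primary event who is still at risk of one.

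The contradiction is certain from the text. The harm is less certain, because it depends on how a site reads Sections 16 and 17 together. About 0.7 to 3 patients per 100 might have a late stroke by month 12, beside about 4 early strokes. The range rests on a constant hazard and on background series that may not match this population. It does not estimate missed primary events. With so few events expected, even one or two patients handled on the wrong definition would be noticeable, so the text should be corrected.

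**What to change.** In Sections 17 and 21.7, replace the descriptions of the primary endpoint with a reference to Section 6.1.

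In Sections 16 and 17, state that no stroke, whether or not it is a primary endpoint, ends the collection of endpoints, scheduled assessments (including end-of-trial CTP and MR), medications and any further revascularization up to month 12.

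Reconcile the two Section 17 paragraphs on treatment after a postoperative ischemic stroke with each other. Which clinical rule applies is for the investigators, and none is proposed here.

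The cost is a short amendment and a few more completed visits and scans in patients who have had a stroke. The visits and the medication record are already in the schedule.

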## 18. Evaluation of End Points and Adverse Events

- **Adverse Event (AE):** An adverse event is the development of an undesirable medical condition or the deterioration of a pre-existing medical condition following or during exposure to a pharmaceutical product or device, whether or not considered causally related to the product. An undesirable medical condition can be symptoms (eg, nausea, chest pain), signs (eg, tachycardia, enlarged liver) or the abnormal results of an investigation (eg, laboratory findings, electrocardiogram). In clinical studies, an AE can include an undesirable medical condition occurring at any time, including run-in or washout periods, even if no study treatment has been administered.
- **Serious Adverse Event (SAE):** A serious adverse event is an AE occurring during any study phase that fulfils one or more of the following criteria:
  - i. Results in death,
  - ii. Is life-threatening,
  - iii. Requires inpatient hospitalization or prolongation of existing hospitalization,
  - iv. Results in persistent or significant disability/incapacity or substantial disruption of the ability to conduct normal life functions,
  - v. Is an important medical event that may jeopardize the patient or may require medical intervention to prevent one of the outcomes listed above.
- **Unanticipated Adverse Device Effect (UADE):** Any serious adverse effect on health

or safety or any life-threatening problem or death caused by or associated with a device, if that effect, problem or death was not previously identified in nature, severity or degree of incidence in the investigational plan or IDE application (including a supplementary plan or application), or any other unanticipated serious problem associated with a device that related to the rights, safety or welfare of subjects.

The following events have been identified as possible complications of revascularization surgery and are considered anticipated:

Vasospasm	Surgical Intervention	Arrhythmia
Vessel dissection	Neurological symptoms	Cardiac ischemia
Vessel occlusion	Pain	Coagulopathy
Vessel perforation	Pseudoaneurysm	Death
Vessel rupture	Renal insufficiency / failure	Emboli (air, tissue, thrombus or foreign body)
Vessel thrombosis	Respiratory Distress / failure	Hematoma, pain, and/or infection at access site
Stroke	Seizure	Hemorrhage
Transient ischemic attack	Infection	Hypertension
Syncope	Drug reaction to antiplatelet medication	Hypotension

## 19. Core Lab

The core lab for imaging assessment is located at Peking University International Hospital. The Digital Imaging and Communications in Medicine (DICOM) imaging data will be collected, transported, and stored according to standardized protocol developed by lab committee. Imaging for diagnosis of MMD, hypoperfusion in the territory of culprit artery, event adjudication will be reviewed by specialists with experience in MR and angiography who are blinded to demographic and clinical characteristics and treatment assignment.

## 20. Quality Assurance

Periodic monitoring and auditing will be performed at each site to ensure that data generated during the study reflect what is specified in the protocol, and data consistency by comparing data in the case report form (CRF) and data collected in source documents for (CRF vs. source documents). If patients who have events go to non-study sites for treatment, source documents will be photocopied for review. It should be guaranteed that the study investigators and relevant study personnel are available during the monitoring visits and possible audits.

## **21. Statistical Consideration**

This section is an overview of the statistical considerations. Complete details can be found in the Statistical Analysis Plan (SAP). It provides the general specifications for the analysis of the data to be collected and presented in the Clinical Study Report. A final SAP will be issued prior to database lock and before code breaking. The SAP will define all “pre-specified, planned analyses.”

### **21.1. Sample size estimates**

Because this trial is a prospective, exploratory, randomized controlled trial, there is no previous data for multimodal neuronavigation guiding precise bypass procedure, the sample size for this trial can't be calculated from the formula. Finally, 100 patients are randomized (1:1) to two groups, 50 of them will undergo direct bypass guided by multimodal neuronavigation, while others will undergo empirical direct bypass procedure.

### **21.2. Description of analysis sets**

All patients who have been randomized to study treatment will be included irrespective of their protocol adherence and continued participation in the study. Patients will be analyzed based on the initial treatment assignment irrespective of whether the event occurred before or following discontinuation of study medication. Patients who withdraw consent to participate in the study will be included up to the date of their study termination except for vital status known through public records (for use in the analysis of all cause death). All efficacy variables will be analyzed using the full analysis set (FAS).

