## 12. Multimodal Neuronavigation Procedure

**Pre-procedure:** All patients randomly assigned to both arms will be suspend aspirin 7 days before the revascularization procedure and restart taking aspirin on the first day postoperatively.

**Intra-procedure:** The surgical procedure will be done under the general anesthesia. ICG fluorescence angiography using Flow800 software and electromagnetic neuronavigation system is required during the procedure of revascularization. An

initial ICG fluorescence angiography will be performed when the dural membrane is unfolded to expose the blood vessels on the surface of the brain. According to the appearance order of vessels to assess the velocity of cerebral flow. Neuronavigation system is used to judge the cerebral hypoperfusion area under different recipient vessels. The vessel was chosen as the receptor with lower flow velocity and lower cerebral perfusion area to perform anastomosis.

Papaverine is used to prevent the occurrence of vasospasm. During surgery, the heparinized water was used to flush the donor's and the receptor's lumen for minimization of thrombosis or thromboembolism risk. An anastomotic end-to-side continuous (or intermittent) suture was performed using a 10-0 nonabsorbable vascular suture thread.

**Post-procedure:** Aspirin 100mg per day must be used for the entire duration of follow-up. Clopidogrel is not necessary after the surgery unless a cardiologist recommends taking clopidogrel for a cardiac indication.

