### **21.3. Statistical Analyses**

All analyses will be based on the intent-to-treat principle using the FAS, including only events adjudicated by the Clinical Events Adjudication Committee (CEC). The primary hypothesis will be tested using a Cox proportional hazards model with a factor for the treatment group. The time to the first event was used in the model when there were multiple events of the same type. P values and Confidence Intervals (CI) for the Hazard Ratio will be obtained according to the Wald statistic. The following statistics, in addition to HR with CI will be also presented in the summary tables of these analyses: the number of patients with event and Kaplan-Meier estimates of the event rate per treatment group calculated at EoT. Kaplan-Meier estimates of the cumulative proportion of patients with primary endpoint events will be calculated and plotted.

The potential impact of loss to follow-up will be evaluated by the sensitivity analysis.

A Cox proportional hazards model will be used to assess differences between study groups in the rate of primary endpoint under the following three scenarios: (1) all patients will be thought to experience primary endpoint event when the final disposition for the event adjudication is not determined. (2) only patients in the empirical bypass arm will be thought to experience primary endpoint event when the final disposition for the event adjudication is not determined. (3) only patients in the multimodal neuronavigation guiding bypass arm will be thought to experience primary endpoint event when the final disposition for the event adjudication is not determined. These results under the three scenarios will be compared with the result under the scenario in which all patients will be not thought to have primary endpoint event when the final disposition for the event adjudication is not determined. However, the primary analysis result will be reported in patients who are censored not to have the event occurrence when the final disposition for the event adjudication is not determined.

The analysis of and the secondary efficacy variable for the test of multimodal neuronavigation guiding bypass against empirical bypass will comprise the confirmatory analysis. No multiplicity adjustment will be made in all analysis including a confirmatory testing (subgroup analysis).

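### Strokes and deaths count only from surgery, although patients are randomized earlier and all are analyzed by intent-to-treat, so pre-operative events are not primary events and an unoperated patient cannot have one

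*Protocol*

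**What the plan says.** Section 6.1 defines the primary endpoint as "All strokes & death within 30 days post-surgery and ipsilateral hemorrhage afterwards". The Synopsis (Section 2) and Section 4 use the same definition.

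Under Sections 9 and 10, the patient consents, is enrolled and receives the allocation, and is operated on afterwards. No longest interval to surgery is given. Section 12 states that patients already assigned to either arm "will be suspend aspirin 7 days before the revascularization procedure".

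Section 21.2 sets the analysis population: "All patients who have been randomized to study treatment will be included irrespective of their protocol adherence". Section 21.3 adds: "All analyses will be based on the intent-to-treat principle using the FAS". The model is stated only as "The primary hypothesis will be tested using a Cox proportional hazards model with a factor for the treatment group", without a time origin. Section 21.8 censors anyone without the event at the end-of-trial visit or at the last contact with full assessment, whichever is earlier. It has no rule for a patient who was not operated on.

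The visit clock in Section 16 starts at randomization ("Study Day 0 day"), and the last interview is "at 12 months (or by telephone) after the recruitment of patients". In Section 6.2, contralateral infarction and TIA on the operated side are also timed from randomization.

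Section 21.7 describes the primary endpoint differently, as stroke or death over one year with no reference to surgery.

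**The concern.** An intent-to-treat comparison follows each patient for the endpoint from randomization. Here the set of patients starts at randomization and the set of countable events starts at surgery. Two groups fall between them.

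- A patient who has a stroke or dies while waiting for surgery has had no primary event.
- A patient never operated on has no 30-day window. Read literally, the later component is closed as well: it follows that window, and a hemorrhage can be ipsilateral only to an operated side.

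Both are analyzed as event-free. In a trial of 100 patients with few expected events, one or two classifications can matter. They should not depend on whether and when surgery took place, because the investigator already knows the allocation when that is decided.

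**Working it through.** **1. Which clock applies.** The visit windows confirm randomization as Day 0. With 30-day months, 90 ± 7 = 83 to 97, 180 ± 14 = 166 to 194 and 360 ± 30 = 330 to 390, exactly as tabulated in Section 16. Only the surgical items (the 30-day stroke and death component, and surgery-related adverse events in Section 6.2) depend on the operation date. For adverse events related to surgery that is natural. For a primary endpoint analyzed in everyone randomized it leaves a gap.

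**2. How three cases are classified.**

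| Case | Section 6.1 | Section 21.7 wording |
|---|---|---|
| Stroke or death after randomization, before surgery | Not an event | Event |
| Stroke or death within 30 days, patient never operated on | Not an event | Event |
| Stroke or death within 30 days after surgery | Event | Event |

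**3. Uncounted strokes.** The protocol gives neither a pre-operative stroke rate nor a waiting time. Assume a wait of d = 7 to 30 days and a constant hazard λ. Expected strokes per 100 patients = 100 × (1 − exp(−λd/365)).

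- Using the 10.1% two-year risk in Section 3: λ = −ln(1 − 0.101)/2 = 0.0532 per year. This gives 0.10 at 7 days, 0.20 at 14 days and 0.44 at 30 days.
- That 10.1% was observed after surgery, so it includes the perioperative peak, put at about 4% per hemisphere in Section 3. Taking this out: λ = −ln(0.899/0.96)/2 = 0.033 per year. This gives 0.06 at 7 days and 0.27 at 30 days.
- Assumed pre-operative rates of 5% to 20% per year give 0.1 to 0.4 at 7 days and 0.4 to 1.8 at 30 days.

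For comparison, the 4% figure implies 100 × 0.04 = 4 strokes in the 30 days after surgery, with one operated hemisphere per patient. Deaths are not in these sums.

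**4. Unoperated patients.** If a share u is never operated on, the observed 30-day rate is the true rate × (1 − u). For a true rate of 4% and assumed u of 2%, 5% or 10%, it becomes 3.92%, 3.80% or 3.60%. If u is equal in both arms, power changes little: for an illustrative 10% against 5% with 50 per arm it falls from 15.5% to 15.3%, 14.9% or 14.3%. If the 10% occurred in one arm only, two equally effective techniques would show a rate ratio of 3.60/4 = 0.90.

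**The case against.** The strongest reply is that the surgery anchor is deliberate. Both arms receive direct bypass from the same surgeon (Section 21.4) and differ only in how the recipient vessel is chosen during the operation. The technique cannot affect a stroke before surgery, so counting it adds noise. This stands as a small cost. Few events would be added, and the plan claims intent-to-treat in everyone randomized, which the present definition does not deliver.

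The wait may also be short. The visit schedule goes from screening and randomization straight to discharge, which fits a single admission, and the aspirin pause is timed from surgery. This is fair, but no section limits the interval.

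Several stronger readings are tempting and are not supported:

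- *That dating at about three months decides which strokes count.* Section 17 requires an adjudication packet within 72 hours of a potential TIA or ischemic stroke. The visit schedule has an event visit, the Synopsis lists a 7-day interview, and strokes are defined by acute onset. What remains is that no visit closes the 30-day window.
- *That the Cox model starts at the wrong time.* The origin is not stated and may be in the SAP. However, no choice of origin turns a pre-operative stroke into an event under Section 6.1.
- *That the stroke count above is a lower bound.* The source risk is post-operative, and entry requires a stable deficit, so the true rate could lie on either side.
- *That the comparison is biased.* The protocol gives no reason to expect delay or cancellation to differ by arm.
- *That a pre-operative stroke cancels the operation under Section 17.* The text advising against bypass after such events may equally concern repeat bypass. It gives no rule for classifying the event.

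**Conclusion.** The point holds as a mismatch in definitions with a small expected effect. Followed as written, Section 6.1 leaves out pre-operative strokes and deaths and makes an unoperated patient event-free by construction, while Sections 21.2 and 21.3 promise an analysis of everyone randomized. Because the gap lies in the endpoint definition, a time origin given in the SAP would not close it. Section 21.7 contradicts the definition and would close it if its wording governed, so the intended endpoint is itself unclear.

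The likely loss is well under one stroke per 100 patients at the protocol's own figures, and up to 1.8 at the highest assumed rate and longest assumed wait. The main effect is lost events and slight dilution. Bias is possible, since allocation is known before surgery, but it is not shown. The wait, the pre-operative rate and the share never operated on are all assumptions. The correction is worth making because it is cheap and aligns the primary endpoint with the stated analysis.

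**What to change.** - Reconcile the primary endpoint across the Synopsis and Sections 4, 6.1 and 21.7. Section 17, which equates the primary endpoint with a stroke in the operated territory, should agree too.
- Define the early component as any stroke or death from randomization through 30 days after surgery or, if no surgery is done, through a fixed window from randomization whose length is stated in advance.
- Record the planned side at randomization, so that ipsilateral is defined for every patient, and start time-to-event at randomization.
- Optionally, add a telephone contact by existing staff 30 days after surgery. Nothing is scheduled between discharge and Day 83 to 97 to close the 30-day window for strokes, deaths and surgery-related adverse events.

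The cost is a protocol amendment with ethics review and, if the contact is added, about 100 short calls. The statistical downside is that a few pre-operative events that the technique cannot affect will be counted, which slightly dilutes the contrast. A supporting analysis restricted to operated patients and timed from surgery would show how much.
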